10.2.3.2 Malignancies

- **Incidence of Malignant or Unspecified Tumours TEAEs per 100 subject years by SOC, HLT and PT**

These events will be presented in the following tables:

- One table will be based on the criteria Standardized MedDRA Query (SMQ) = “Malignant or unspecified tumours (SMQ)”
- One table will be based on the criteria SMQ = “Malignant tumours (SMQ)”.

SMQ search will include all TEAEs which code to a PT included in the Scope=Narrow group within each SMQ.

Note that the events included in the “Malignancies” table will be a subset of the events included in the “Malignancies (including unspecified)” table. While the “Malignant tumours (SMQ)” is most relevant, “Malignant or unspecified tumours (SMQ)” must be reviewed for potential malignancies.

The output tables will include 2 different overall incidence rows:

- The first overall incidence row will summarize “Any Malignancy” and this row will summarize the incidence of all AEs flagged for inclusion in the table (using the appropriate SMQ depending on the table), regardless of the HLT it codes to.
- The second overall incidence row will summarize “Any Malignancy excluding non melanomic skin cancers HLT” and this row will summarize the incidence of AEs flagged for inclusion in the table (using the appropriate SMQ depending on the table), excluding those which code to an HLT of “skin neoplasms malignant and unspecified (excl melanoma)”.

10.2.3.3 Major adverse cardiac event

- **Incidence of Adjudicated Major Cardiac Event (MACE) TEAEs per 100 subject years by SOC, HLT and PT**

Potential cardiovascular events are adjudicated by the independent Cardiovascular Event Adjudication Committee (CV-CAC) according to the CV-CAC Charter (version 6.0). Adjudicated events are classified by the CV-CAC to one of the event types as defined in [Table 10–1](#). The classification of an event as a Major Adverse Cardiac Event (MACE) is also determined by the CV-CAC. Events which are classified by the CV-CAC as any of the event types identified in the third column of [Table 10–1](#) will be considered an extended MACE. Note that extended MACE is determined programmatically and includes a broader scope definition of MACE.

MACE as determined by the CV-CAC will be presented in a table and listing. Extended MACE will be presented separately in a table and listing.

Another table and listing will present the adjudicated cardiovascular events by type. For each cardiovascular event type, the individual PTs which fall within each event type will be summarized. This listing will indicate whether each event was determined to be a MACE and/or an extended MACE.

Additionally, a listing of all events identified for potential review by the CV-CAC will be produced. This listing will indicate whether each event was identified by the CV-CAC Chair for full committee review.

Table 10–1: Cardiovascular event classifications

Event Type Code	Event Type	Extended MACE
1	Non-Fatal Myocardial Infarction (MI)	Yes
2	Non-Fatal Stroke: hemorrhagic	Yes
3	Non-Fatal Stroke: ischemic	Yes
4	Non-Fatal Stroke: embolic	Yes
5	Non-Fatal Stroke: undeterminable	Yes
6	Hospitalization or ER for Unstable Angina with urgent revascularization	Yes
7	Hospitalization or ER for Unstable Angina without urgent revascularization	No
8	Hospitalization for Heart Failure	Yes
9	Transient Ischemic Attack (TIA)	No
10	Coronary Revascularization Procedures (e.g. percutaneous coronary intervention, coronary artery bypass grafting)	Yes
11	Urgent Revascularization Procedures (i.e. due to symptoms of brain ischemia or pending infarction)	Yes
12	Arrhythmia (not associated with ischemia)	No
13	Peripheral Arterial Event	No
14	Venous Thromboembolic Event: pulmonary embolism (PE)	No
15	Venous Thromboembolic Event: deep vein thrombosis (DVT)	No
16	Venous Thromboembolic Event: PE and DVT	No
17	Other CV Event	No
18	Death due to Myocardial Infarction (MI)	Yes
19	Death due to Stroke	Yes
20	Sudden Cardiac Death	Yes

Table 10–1: Cardiovascular event classifications

Event Type Code	Event Type	Extended MACE
21	Other CV Death (e.g. heart failure, pulmonary embolism, cardiovascular procedure-related)	Yes
22	Cardiovascular: Undetermined Cause of Death (i.e. cause of death unknown)	Yes
23	Non-Cardiovascular Death	No
24	Non-Cardiovascular Event	No
99	Inadequate information to adjudicate	No

CV=Cardiovascular; DVT=Deep Vein Thrombosis; ER=Emergency Room; MACE=Major Adverse Cardiac Event; MI=Myocardial Infarction; PE=Pulmonary Embolism; TIA=Transient Ischemic Attack.

MACE is determined by the adjudication committee and is not identified programmatically based on event type.

10.2.3.4 Neutropenia

- **Incidence of Neutropenia TEAEs per 100 subject years by SOC, HLT and PT**

This table will be based on the following PTs (regardless of seriousness):

- Autoimmune neutropenia
- Band neutrophil count decreased
- Cyclic neutropenia
- Febrile neutropenia
- Idiopathic neutropenia
- Neutropenia
- Neutropenic infection
- Neutropenic sepsis
- Neutrophil count decreased

10.2.3.5 Suicidal Ideation and Behavior

- **Incidence of Suicidal Ideation or Behavior TEAEs per 100 subject years by SOC, HLT and PT**

Potential neuropsychiatric events are adjudicated by the independent Neuropsychiatric Adjudication Committee according to the Neuropsychiatric Adjudication Committee (version 8.0). Adjudicated events are classified by the Committee as Suicidal or Non-suicidal.

Adjudicated events are also further classified by the Committee to one of the event types as defined in [Table 10–2](#). Suicidal Ideation and Behavior (SIB) is defined as events classified by the Committee as Suicidal.

A table and listing will present SIB events.

Another table and listing will present the adjudicated neuropsychiatric events by type. For each neuropsychiatric event type, the individual PTs which fall within each event type will be summarized. This listing will indicate whether each event was determined to be Suicidal or Non-Suicidal. For event type suicidal ideation, the listing will also indicate if intent was present and if the suicidal ideation was clinically significant.

Additionally, a listing of all events identified for potential review by the Committee will be produced. This listing will indicate whether each event was identified by the Neuropsychiatric Event Adjudication Committee Chair for full committee review.

Table 10–2: Neuropsychiatric event classifications

Event Type Code	Event Classification	Event Type
1	Suicidal	Suicidal events/completed suicide
2	Suicidal	Suicide attempt
3	Suicidal	Preparatory acts toward imminent suicidal behavior
4	Suicidal/Non-suicidal ^a	Suicidal ideation
7	Non-suicidal	Nonsuicidal Self-injurious behavior
8	Non-suicidal	Nonsuicidal Other
99	Not applicable	Inadequate information to adjudicate

^a Suicidal ideation event types can be classified by the Neuropsychiatric Adjudication Committee as Suicidal or Non-suicidal depending on whether intent to die was present.

10.2.3.6 Inflammatory bowel disease

- Incidence of Inflammatory Bowel Disease TEAEs per 100 subject years by SOC, HLT and PT**

Selected gastrointestinal events are adjudicated by the independent Inflammatory Bowel Disease (IBD) Adjudication Committee (IBD-CAC) according to the IBD-CAC Charter (version 3.0). Adjudicated events are classified by the IBD-CAC into one of the diagnostic types as defined in [Table 10–3](#). The events will further be classified as definite, probable or possible IBD.

An overview of adjudicated IBD events will be stratified by subjects with or without a previous medical history of IBD. Previous medical history of IBD will be determined using the information recorded on the History of IBD CRF page ("Does subject have a history of IBD?"). This overview table will present events adjudicated by the IBD-CAC as either possible, probable or definite IBD. Definite and probable IBD will also be aggregated and summarized in this table. In addition, this table will summarize each IBD event classification (possible, probable or definite) separately.

Another table and listing will present the adjudicated IBD events by type. For each IBD event type, the individual PTs which fall within each event type will be summarized.

Additionally, a listing of all events identified for potential review by the IBD-CAC will be produced. This listing will indicate whether each event was identified by the IBD-CAC Chair for full committee review.

A further supportive listing will present the individual diagnostic criteria met for each adjudicated IBD event.

Table 10–3: IBD event classifications

Event Type Code	Event Type (Classification and diagnosis)	Classification
1	Possible Inflammatory Bowel Disease – Crohn’s Disease	Possible
2	Probable Inflammatory Bowel Disease – Crohn’s Disease	Probable
3	Definite Inflammatory Bowel Disease – Crohn’s Disease	Definite
4	Possible Inflammatory Bowel Disease – Ulcerative Colitis	Possible
5	Probable Inflammatory Bowel Disease – Ulcerative Colitis	Probable
6	Definite Inflammatory Bowel Disease – Ulcerative Colitis	Definite
7	Possible Inflammatory Bowel Disease – type unclassified	Possible
8	Probable Inflammatory Bowel Disease – type unclassified	Probable
9	Definite Inflammatory Bowel Disease – type unclassified	Definite
10	Symptoms not consistent with Inflammatory Bowel Disease	Not applicable
11	Possible Inflammatory Bowel Disease – Microscopic Colitis	Possible
12	Probable Inflammatory Bowel Disease – Microscopic Colitis	Probable
13	Definite Inflammatory Bowel Disease – Microscopic Colitis	Definite
14	Possible Inflammatory Bowel Disease – no further differentiation possible	Possible
15	Probable Inflammatory Bowel Disease – no further differentiation possible	Probable
16	Definite Inflammatory Bowel Disease – no further differentiation possible	Definite
99	Not enough information to adjudicate	Not applicable

IBD=inflammatory bowel disease.

Note: IBD diagnoses of “microscopic colitis” and “no further differentiation possible” were added in an adjudication charter amendment, accounting for the event type numbering.

10.2.3.7 Hypersensitivity (including anaphylaxis)

- **Incidence of Anaphylactic Reaction TEAEs per 100 subject years by SOC, HLT and PT**

A separate table will be prepared based on the MedDRA anaphylaxis Algorithm (see Appendix 1) for acute anaphylactic events (reported on the same day as when an injection was administered or 1 day after). An AE glossary table will also be produced to summarize the MedDRA coding for these events. The glossary table will include the following fields: reported term, PT, LLT, HLT, and SOC.

A separate table will be prepared to summarize hypersensitivity events, identified using the SMQ “Hypersensitivity (SMQ)”. All TEAEs which code to a PT included in the Scope=Narrow search will be included in this table. In addition, a separate table will be prepared to summarize serious hypersensitivity events, identified using the SMQ “Hypersensitivity (SMQ)”. All serious TEAEs which code to a PT included in the Scope=Narrow search will be included in this table. An AE glossary table will also be produced to summarize the MedDRA coding for these events. The glossary table will include the following fields: reported term, PT, LLT, HLT, and SOC.

Furthermore, a separate table will be prepared to summarize injection site reactions, identified using the HLTs: “Administration site reactions NEC” and “Injection site reactions”.

10.2.3.8 Hepatic events and PDILI

- **Incidence of hepatic events TEAEs per 100 subject years by SOC, HLT and PT**

A table for hepatic events will be created based on the SMQ of “Drug related hepatic disorders - comprehensive search (SMQ)”. However, these 2 sub-SMQs are to be excluded: “Liver neoplasms, benign (incl cysts and polyps) (SMQ)” and “Liver neoplasms, malignant and unspecified (SMQ)”. For each of the above SMQs, include all TEAEs which code to a PT included in the Scope=Broad and/or Scope=Narrow.

Note that all AEs meeting the above criteria are to be included. It will not be limited to events that the investigator determined to be related to study drug.

Cases of potential Hy’s Law will be reported separately in a liver function test table.

10.3 Clinical laboratory evaluations

Laboratory values, including markedly abnormal laboratory values will be presented descriptively by treatment group for the SS, MS, and AMS.

The markedly abnormal tables and those based on common terminology criteria for AEs (CTCAE) grade will be produced only for selected laboratory variables.

For tables where data are summarized by visit, unscheduled and repeat visits will not be summarized, but these data will be included in listings. For tables where multiple measurements over a period of time are considered (as in shift tables), unscheduled and repeat visits will be considered as long as they were collected in the period being summarized (values observed more than 140 days after the last administration of study medication are not considered). All summaries will be presented in SI units and will be based on observed case values. In the case where laboratory values are below the LLQ, then these will be set to the midpoint between 0 and the lower limit of quantification for the purpose of summarizing the data. The following summaries are required:

- A summary of the absolute and change from Baseline values in each laboratory variable by treatment group and visit

- A summary of the number and percentage of participants experiencing markedly abnormal values at any time while on treatment (assessment on or following the first dose of study treatment through the minimum of period of interest (Week 16) or date of last dose + 140 days) by laboratory variable and treatment group. Two separate tables will show results for the Initial Treatment Period (for the SS) and the Initial and Maintenance Treatment Period (for the AMS).
- A summary of the number and percentage of participants with a given CTCAE grade (0,1,2,3, or 4) based on minimum/maximum post-baseline value by laboratory variable and treatment group. Two separate tables will show results for the Initial Treatment Period (for the SS) and the Initial and Maintenance Treatment Period (for the AMS).
- A shift table of the number and percentage of participants experiencing CTCAE grade 0,1,2,3, or 4 values (as applicable) at Baseline to maximum post-Baseline CTCAE grade, by laboratory variable and treatment group. Two separate tables will show results for the Initial Treatment Period (for the SS) and the Initial and Maintenance Treatment Period (for the AMS).
- A by-participant listing of all laboratory data (including urinalysis) will be provided. This listing will be presented by treatment group and will include: center, participant identifier, age, sex, race, weight, visit, laboratory variable, result (with abnormal values flagged as “L” or “H” accordingly) and unit.

Markedly abnormal values are defined as those with a severity of Grade 3 and above based on the CTCAE criteria Version 4.03. Definitions of markedly abnormal values using the Grade 3 cut points are given in the tables below for age ranges of ≥ 17 years [Table 10–4](#) for markedly abnormal liver function test values, [Table 10–5](#) for markedly abnormal biochemistry values and [Table 10–6](#) for markedly abnormal hematology values). Tables summarizing markedly abnormal values will include a summary (counts and percentages) of markedly abnormal labs observed at any time while on treatment (ie, treatment-emergent markedly abnormal [TEMA]). For this summary, Baseline values and values observed more than 140 days after the last administration of study medication are not considered. The laboratory results classified as Grade 3 or Grade 4 will be summarized and listed separately.

Table 10–4: Definitions of Markedly Abnormal Liver Function Values

Parameter name	Conventional		Standard		Abnormal Designation
	Unit	Criteria	Unit	Criteria	
ALP	U/L	>5.0 x ULN	U/L	>5.0 x ULN	AH
ALT	U/L	>5.0 x ULN	U/L	>5.0 x ULN	AH
AST	U/L	>5.0 x ULN	U/L	>5.0 x ULN	AH
Total Bilirubin	mg/dL	>3.0 x ULN	umol/L	>3.0 x ULN	AH
GGT	U/L	>5.0 x ULN	U/L	>5.0 x ULN	AH

Table 10–5: Definitions of Markedly Abnormal Biochemistry Values

Parameter name	Conventional		Standard		Abnormal Designation
	Unit	Criteria	Unit	Criteria	
Creatinine ¹	mg/dL	> 3.0 x Baseline or >3.0 x ULN	umol/L	> 3.0 x Baseline or >3.0 x ULN	AH
Glucose	mg/dL	<40 >250	mmol/L	<1.7 >13.9	AL AH
Calcium	mg/dL	>12.5 <7.0	mmol/L	>3.1 <1.75	AH AL
Magnesium	mg/dL	>3.0 <0.9	mmol/L	>1.23 <0.4	AH AL
Potassium	mmol/L	>6.0 <3.0	mmol/L	>6.0 <3.0	AH AL
Sodium	mmol/L	>155 <130	mmol/L	>155 <130	AH AL
Cholesterol	mg/dL	>400	mmol/L	>10.34	AH

¹ The markedly abnormal definitions for creatinine are based on the logical or, if either criterion is met the creatinine value will be designated as abnormal high.

Table 10–6: Definitions of Markedly Abnormal Hematology Values

Parameter name	Conventional		Standard		Abnormal Designation
	Unit	Criteria	Unit	Criteria	
Hemoglobin	g/dL	<8.0 >4.0 above ULN	g/L	<80 >40 above ULN	AL AH
Lymphocytes Absolute	10 ⁹ /L	<0.5 >20.0	10 ⁹ /L	<0.5 >20.0	AL AH
Neutrophils Absolute	10 ⁹ /L	<1.0	10 ⁹ /L	<1.0	AL
Platelets	10 ⁹ /L	<50	10 ⁹ /L	<50	AL
WBC/Leukocytes	10 ⁹ /L	<2.0 >100	10 ⁹ /L	<2.0 >100	AL AH

Abbreviations: AH=abnormal high; AL=abnormal low; ALP = alkaline phosphatase; ALT= alanine aminotransferase; AST = aspartate aminotransferase; dL = deciliter; GGT: gamma-glutamyltransferase; L = liter; mg = milligram; mmol = millimoles; µg = microgram; ULN = upper limit of normal, WBC=white blood cells.

The table for markedly abnormal liver function tests (LFTs) will contain data beyond the CTCAE Grade 3 thresholds outlined in [Table 10-1](#) above in order to allow for a more thorough review of elevated LFTs. There will be 1 table, which will list the count and percentage of participants meeting the below criteria at any time during the study:

- AST: >3xULN, >5xULN, >8xULN, >10xULN, >20xULN
- ALT: >3xULN, >5xULN, >8xULN, >10xULN, >20xULN
- AST or ALT: >3xULN, >5xULN, >8xULN, >10xULN, >20xULN
- Total Bilirubin: >1.5xULN, >2xULN
- ALP: >1.5xULN

For any participant with at least one markedly abnormal LFT (AST >3xULN, ALT >3xULN, bilirubin >3xULN, or ALP >1.5xULN) the New Ratio (nR) will be calculated as the ratio of either ALT or AST (whichever is higher) to ALP, all expressed as multiples of their ULN as follows:

- $nR = [\text{maximum}(\text{AST}/\text{ULN or ALT}/\text{ULN})]/(\text{ALP}/\text{ULN})$

Any pDILI will be summarized (all criteria must be met at the same assessment):

- (AST or ALT > 3xULN) and Total Bilirubin > 1.5xULN
- (AST or ALT > 3xULN) and Total Bilirubin > 2xULN

In addition, a table will be produced to summarize potential Hy's Law cases. The following definition will be used in that table:

- $[\text{AST} \geq 3\text{xULN or ALT} \geq 3\text{xULN}] \text{ and Total Bilirubin} \geq 2\text{xULN}$ in the absence of ALP $\geq 2\text{xULN}$

In order to meet the above potential Hy's Law criteria, a participant must experience the elevation in bilirubin and ALT or AST (and the absence of ALP elevation, if applicable) at the same assessment. For example, a participant who experiences a ≥ 2 x ULN elevation of bilirubin at one visit and a ≥ 3 xULN elevation in ALT (or AST) at a subsequent visit has not fulfilled the Hy's Law criteria.

Potential hepatotoxicity (meeting one of the PDILI or Hy's Law laboratory criteria at least once) will be considered with and without symptoms potentially associated with hepatitis or hypersensitivity according to the investigator (reported on the Symptoms of Hepatitis and Hypersensitivity CRF page).

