10.4 Vital signs, physical findings, and other observations related to safety

10.4.1 Vital signs

The following vital signs variables will be summarized: systolic blood pressure (mmHg), diastolic blood pressure (mmHg), body temperature (°C) and heart rate (beats/min). The following summaries will be provided for the SS:

- A summary of the absolute and change from Baseline value for each vital sign variable by treatment group and visit.
- A summary of the number and percentage of participants experiencing at least 1 markedly abnormal value for a vital sign variable as defined in Table 10–7, by treatment group and period (Initial Treatment Period [SS], and Initial and Maintenance Treatment Period [AMS]). Unscheduled and repeat visits will be considered as long as they were collected in the period being summarized (values observed more than 140 days after the last administration of study medication are not considered).

Table 10–7: Definitions of Markedly Abnormal Blood Pressure Values

Parameter (unit)	Markedly Abnormal Low	Markedly Abnormal High
Systolic blood pressure (mmHg)	<90 and a decrease from Baseline of ≥ 20	>180 and an increase from Baseline of ≥ 20
Diastolic blood pressure (mmHg)	<50 and a decrease from Baseline of ≥ 15	>105 and an increase from Baseline of ≥ 15

A by-participant listing of all vital signs data will be provided. This listing will be presented by treatment group and will include: center, participant identifier, age, sex, race, weight, visit, vital sign variable and result (with abnormal values flagged as “L” or “H” accordingly).

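### Laboratory values are labelled treatment-emergent markedly abnormal without reference to Baseline status, so abnormalities already present at Baseline can be counted as emergent

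*SAP*

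**What the plan says.** Section 10.3 fixes the threshold first: "Markedly abnormal values are defined as those with a severity of Grade 3 and above based on the CTCAE criteria Version 4.03". The cut points are in Tables 10-4 (liver tests), 10-5 (biochemistry) and 10-6 (hematology).

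The tables of markedly abnormal values then summarize "markedly abnormal labs observed at any time while on treatment (ie, treatment-emergent markedly abnormal [TEMA"). The window is "assessment on or following the first dose of study treatment through the minimum of period of interest (Week 16") or 140 days after the last dose, whichever is earlier. The only exclusions are in this sentence: "For this summary, Baseline values and values observed more than 140 days after the last administration of study medication are not considered".

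One laboratory criterion in Tables 10-4 to 10-6 mentions Baseline. Creatinine is flagged above 3 times Baseline or above 3 times ULN, and "if either criterion is met the creatinine value will be designated as abnormal high".

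Baseline grade is used in a separate output, a shift table of CTCAE grade "at Baseline to maximum post-Baseline CTCAE grade, by laboratory variable and treatment group". Section 10.3 also requires change-from-Baseline summaries, separate summaries and listings of Grade 3 and Grade 4 results, and a by-participant listing of all laboratory data.

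**The concern.** A reader takes a treatment-emergent count to mean abnormalities that were new or had worsened after dosing began. The SAP uses the term that way for adverse events: under Section 10.2.1 a TEAE must start on or after the first dose. The laboratory rule has no equivalent condition. It asks when the sample was taken, not whether the abnormality arose after dosing.

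What is at stake is the accuracy of a descriptive safety count. Abnormalities that pre-date treatment are added to the reported incidence in every arm under a label that says they emerged on treatment.

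**Working it through.** The plan gives no figure to reproduce, so the check has three parts.

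**1. Apply the rule to each Baseline and on-treatment pattern.** Neutrophils serve as the example: the Table 10-6 cut is below 1.0 x 10^9/L; in Table 12-2, Grade 3 is 0.5 to below 1.0 and Grade 4 is below 0.5. The participant values are illustrative.

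| Baseline | On treatment | Counted? | Emergent in fact? |
|---|---|---|---|
| 2.0 | 0.8 | Yes | Yes |
| 0.8 (Grade 3) | 0.8 (Grade 3) | Yes | No, unchanged |
| 0.4 (Grade 4) | 0.8 (Grade 3) | Yes | No, improved |
| 0.8 (Grade 3) | all 1.2 or higher | No | No |

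Rows 2 and 3 are the error. Row 4 marks its limit: a Baseline abnormality enters the count only if at least one on-treatment value is also beyond the cut. The creatinine criterion does not prevent the error, because its two limbs are joined by or and the ULN limb alone is enough.

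**2. Size, under assumptions.** From Section 2.4, bimekizumab N = 3 x 140 = 420 and placebo N = 70. Assumed, because the SAP gives neither: a proportion b = 0.1% to 2% of participants beyond the cut at Baseline for a given analyte, and a proportion k = 70% of those beyond it again on treatment.

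Expected over-count = N x b x k:
- Bimekizumab: 420 x 0.001 x 0.7 = 0.3, up to 420 x 0.02 x 0.7 = 5.9.
- Placebo: 70 x 0.001 x 0.7 = 0.05, up to 70 x 0.02 x 0.7 = 1.0.

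Effect on the comparison: let p be the true new incidence among those not beyond the cut at Baseline. The reported proportion in an arm is (1 - b) x p + b x k. With b and k equal across arms, the b x k term cancels and the reported difference is (1 - b) x (p_BKZ - p_PBO). That is 0.98 to 0.999 of the true difference for b between 2% and 0.1%.

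**3. Hemoglobin, Table 10-6 against Table 12-2.** Markedly abnormal is meant to be Grade 3 and above. Table 10-6 flags high hemoglobin at more than 40 g/L above ULN only. Table 12-2 measures from Baseline when Baseline is above ULN. Take Baseline 10 g/L above ULN and an on-treatment value 41 g/L above ULN. Table 10-6 gives 41 > 40, markedly abnormal. Table 12-2 gives 41 - 10 = 31 above Baseline, Grade 2. The two tables classify the same value differently.

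**The case against.** The strongest reply is that Section 10.3 defines its term where it is used, can be programmed as written, and answers the worsening question elsewhere through the shift table, the change-from-Baseline summaries and the listings. Much of this stands: the information is partly recoverable and the tables are descriptive. Two things remain. The other outputs leave the count and its label uncorrected. And Tables 12-1 and 12-2 as shown contain no grades for glucose or for the liver tests, so for those analytes recovery may depend on reading listings.

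A reader might infer more than the documents support:

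- **That the plan instructs the analyst to disregard Baseline as a comparator.** The sentence "Baseline values and values observed more than 140 days after the last administration of study medication are not considered" governs which samples may count as events. It properly stops a Baseline sample from being counted. The fault is that no comparator is specified anywhere else.
- **That the difference between bimekizumab and placebo is diluted.** In expectation the risk difference is almost unchanged, as shown above. Only a ratio of incidences would shrink noticeably, and Section 10.3 plans none. Chance imbalance is possible, since one persistent case among 70 on placebo is 1.4%, but that is not systematic dilution.
- **That counts are inflated 1.7 to 2.4 times.** That range needs a Baseline prevalence of 1% to 2%, 70% persistence and a true new incidence of 1% (4.2 of 420), none of which the SAP gives. At 0.1% prevalence the ratio is (4.2 + 0.3)/4.2 = 1.07.
- **That this is the main laboratory safety table.** It is one of several required summaries.
- **That the blood pressure rule proves an inconsistency.** Table 10-7 ("Definitions of Markedly Abnormal Blood Pressure Values") does require a change from Baseline, but it defines markedly abnormal, not treatment-emergent, and uses no CTCAE grades. The TEAE onset rule is the better comparison.

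**Conclusion.** The point holds as a minor, real fault of definition. As written, the rule counts unchanged or improving Baseline Grade 3 to 4 abnormalities as treatment-emergent and so overstates that incidence in each arm. The size cannot be estimated from the documents and may be small: about 0.3 to 6 of 420 bimekizumab participants per analyte if Baseline prevalence is 0.1% to 2% and persistence is 70%. The near-unchanged risk difference rests on randomization and on similar persistence across arms. No efficacy, multiplicity or formal safety inference is affected. The hemoglobin mismatch is a separate small inconsistency in the same definitions.

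**What to change.** In Section 10.3:

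1. Where the SAP tabulates grades, define TEMA as an on-treatment Grade 3 or 4 value with a grade higher than the participant's Baseline grade. A move from Grade 3 to Grade 4 then counts, and a persistent Grade 3 does not.
2. Where it tabulates none (liver tests, glucose), define TEMA as an on-treatment value meeting the Table 10-4 or 10-5 cut when the Baseline value did not meet it. The same form can use the Table 10-6 cut for any hematology parameter without grades.
3. State how a missing Baseline value is handled.
4. Show participants already beyond the cut at Baseline separately.
5. Reconcile the high-hemoglobin cut in Table 10-6 with Table 12-2.

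At minimum, relabel the summary as post-Baseline markedly abnormal and present it by Baseline status.

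The cost is a few sentences and one Baseline-status flag. The Baseline values are already needed for the change-from-Baseline summaries. For graded parameters the Baseline grade is already needed for the shift table; for liver tests and glucose the flag has to be derived from the cut points.

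### Table 10-5 gives two low-glucose limits that are not equivalent (<40 mg/dL is about <2.2 mmol/L; <1.7 mmol/L is about <31 mg/dL), and they need to be reconciled

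*SAP*

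**What the plan says.** Section 10.3 states the rule behind its threshold tables: "Markedly abnormal values are defined as those with a severity of Grade 3 and above based on the CTCAE criteria Version 4.03". It adds: "Definitions of markedly abnormal values using the Grade 3 cut points are given in the tables below". Table 10-5 then carries the biochemistry limits, with a conventional-unit column and a standard-unit column side by side. The glucose row reads "Glucose mg/dL <40 >250 mmol/L <1.7 >13.9", with the first value of each pair designated abnormally low and the second abnormally high.

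The limits feed this output: "A summary of the number and percentage of participants experiencing markedly abnormal values at any time while on treatment". It is produced once for the Initial Treatment Period on the Safety Set and once for the combined Initial and Maintenance Treatment Period on the Active Medication Set. On units, the same section says: "All summaries will be presented in SI units and will be based on observed case values".

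The CTCAE grade tables in Appendix B (Section 12.2) have no glucose row. Nothing else in the current text gives a glucose grade boundary.

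**The concern.** A row with two unit columns should state one criterion twice. If the two cells are different concentrations, the definition of markedly low glucose depends on which column the programmer reads. Two programmers working from different columns could report different counts from the same data, and the plan gives no rule for choosing between them.

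At stake is the count of participants with markedly low glucose in two safety tables. Section 10.3 refers to the Grade 3 cut point as a single boundary, and at most one of the two printed limits can be that boundary.

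**Working it through.** **Inputs (SAP, Table 10-5).** Low glucose: 40 mg/dL and 1.7 mmol/L. High glucose: 250 mg/dL and 13.9 mmol/L.

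**Step 1. Take the conversion factor from the row itself.** Factor = (mg/dL) / (mmol/L).
- High pair: 250 / 13.9 = 17.99, i.e. 18.0 mg/dL per mmol/L.
- Low pair: 40 / 1.7 = 23.5 mg/dL per mmol/L.

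One analyte has one factor, so the two pairs cannot both be right. As an outside check, the molar mass of glucose (180.156 g/mol, a physical constant that the SAP does not give) yields 180.156 / 10 = 18.016. This supports the high pair: 250 / 18.016 = 13.88, printed as 13.9.

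**Step 2. Convert the low limits with that factor.**
- 40 / 17.99 = 2.22 mmol/L, against 1.7 printed.
- 1.7 × 17.99 = 30.6 mg/dL, against 40 printed.
- Gap: 2.22 − 1.7 = 0.52 mmol/L, or 40 − 30.6 = 9.4 mg/dL. Relative to the converted limit, 0.52 / 2.22 = 23%.

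Varying the factor from 18 to 18.2 moves the results only to 2.20–2.22 mmol/L and 30.6–30.9 mg/dL.

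**Step 3. Rule out rounding.** A printed 1.7 can stand for anything up to 1.75, and 1.75 × 18.0 = 31.5 mg/dL, still well short of 40. Rounded to one decimal, 40 mg/dL is 2.2 mmol/L, not 1.7.

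**Step 4. Check the other mg/dL to mmol/L pairs in Table 10-5** (molar masses are again physical constants: calcium 40.078, magnesium 24.305, cholesterol 386.654 g/mol).

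| Parameter | mg/dL | Converted, mmol/L | Printed, mmol/L | Difference |
|---|---|---|---|---|
| Glucose, low | 40 | 2.22 | 1.7 | −23.4% |
| Glucose, high | 250 | 13.88 | 13.9 | +0.2% |
| Calcium, high | 12.5 | 3.12 | 3.1 | −0.6% |
| Calcium, low | 7.0 | 1.747 | 1.75 | +0.2% |
| Magnesium, high | 3.0 | 1.234 | 1.23 | −0.3% |
| Magnesium, low | 0.9 | 0.370 | 0.4 | +8.0% |
| Cholesterol, high | 400 | 10.345 | 10.34 | −0.0% |

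Low magnesium agrees only at one decimal, which is coarse. Low glucose is the only pair that rounding cannot reconcile.

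**Step 5. Identify the values affected.** A glucose value from 1.7 up to about 2.2 mmol/L (about 31 to just under 40 mg/dL) meets the conventional limit and fails the SI limit. Outside that band the two limits classify every value alike.

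**The case against.** The mismatch itself has no good defence. It is not an artefact of the PDF conversion: the amendment log reproduces the same glucose pair where it describes the revision of this table (Section 13.1, Change #73). The arguments on the other side concern what follows from it.

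- **Which cell is wrong.** A reader might infer that <40 mg/dL is the true criterion and <1.7 mmol/L the mistake. The SAP does not show this. It names the CTCAE version but prints no glucose grades, so either cell could be in error. This objection stands.
- **Whether anyone is missed.** A reader might also infer that low-glucose events will be under-reported in every treatment group. That needs <40 mg/dL to be the right limit and participants to have values in the band. The SAP gives no glucose data or expected frequency, so the number affected could be zero in any or all arms. This stands too.
- **Which column is applied.** The SI-units sentence governs presentation and does not say which column drives the classification. It makes use of the SI column likely, not certain.
- **Listing flags.** A reader might extend the problem to the by-participant listing. That listing marks values L or H, whereas Table 10-5 uses AL and AH, and nothing ties the two together. The listing should be left out of the point.
- **Visibility.** All laboratory values are listed, and the by-visit summaries include the minimum (Section 3.1). A value in the band would therefore still appear in the report; only its place in the markedly abnormal count is in doubt. This limits the harm but leaves the definition unsettled.
- **Priority.** Low glucose is not among the safety topics of interest in Section 2.2.3.2, and no test, alpha, sample size or efficacy endpoint depends on it. That is a fair argument for modest priority.

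**Conclusion.** The point holds as an internal contradiction. The two low-glucose limits in Table 10-5 differ by about 0.5 mmol/L (about 9 mg/dL, or 23%), so at least one is wrong as a statement of the Grade 3 cut point. The arithmetic needs only the SAP's own high-glucose pair.

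The consequence is conditional on three things: that the SI column is the one applied, which Section 10.3 makes likely; that <40 mg/dL is the intended cut point; and that some participant has a lowest post-Baseline value from 1.7 up to about 2.2 mmol/L. If all three hold, that participant is left out of the markedly abnormal count for whichever of the two periods contains the value. If <1.7 mmol/L is the intended cut point and is the limit applied, the SI tables are right and only the conventional cell misleads. Either way the effect stays within descriptive safety tables.

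**What to change.** Reconcile the two low-glucose limits in Table 10-5 with each other and with the CTCAE 4.03 Grade 3 cut point that Section 10.3 names:

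- if <40 mg/dL stands, the SI limit is <2.2 mmol/L;
- if <1.7 mmol/L stands, the conventional limit is about <31 mg/dL.

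Then program the markedly abnormal tables for the Initial and the combined period from the reconciled value. The cost is one table cell and one programming constant, with no new data.
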